2.8.2 Deaths

Summaries for on-treatment and all deaths will be produced separately by SOC, PT, and treatment. Deaths will be listed with post treatment deaths flagged. A listing of deaths prior to starting treatment will be provided for all screened subjects.

2.8.3 Laboratory data

On analyzing laboratory, data from all sources, including central and local laboratories, will be combined. The summaries will include all assessments available for the lab parameter collected no later than 130 days after the last study treatment administration date. Grading of laboratory values will be assigned programmatically per NCI CTCAE 5.0. The time windows for lab assessments are shown in [Table 2-7](#):

Table 2-7 Time windows for lab assessments

Time Window	Planned Visit Timing	Time Window Definition
On treatment		
Baseline	On or before Study Day 1[a]	≤ Study Day 1
Week 3	Study Day 22	Study Days 2 to 32
Week 6	Study Day 43	Study Days 33 to 53
.....
Week k (with k = 9,12 ...)	Study Day 21*(k/3)+1	Study Day 21*(k/3)-9 to 21*(k/3)+11
Safety follow-up 1	26 days after treatment discontinuation	[EOT visit date+8; EOT date +39]
Safety follow-up 2	52 days after treatment discontinuation	[EOT visit date+40; EOT date +65]
Safety follow-up 3	78 days after treatment discontinuation	[EOT visit date+66; EOT date +91]
Safety follow-up 4	104 days after treatment discontinuation	[EOT visit date+92; EOT date +117]
Safety follow-up 5	130 days after treatment discontinuation	[EOT visit date+118; EOT date +143]

[a] Study Day 1 = first treatment date

The following summaries will be produced for hematology and biochemistry laboratory data by laboratory parameter and treatment:

- Worst post-baseline CTC grade, regardless of the baseline status. Each subject will be counted only for the worst grade observed post-baseline
- Shift tables using CTC grades to compare baseline with the worst on-treatment value. Hypo and hyper worst grade will be summarized separately if applicable
- For laboratory tests where CTC grades are not defined, shift tables using the low/normal/high classification to compare baseline with the worst on-treatment value
- Trends of lab parameter values over time, including baseline and selected on-treatment time points, will be displayed via boxplots

The following listings will be produced for the laboratory data:

- Listings of all laboratory data, with CTC grades and classification relative to the laboratory normal range. Lab data collected during the post-treatment period will be flagged
- Listing of all CTC grade 3 or 4 laboratory toxicities

Liver function parameters

Liver function parameters of interest are total bilirubin (TBL), ALT, AST, and alkaline phosphatase (ALP). The number (%) of subjects with worst post-baseline values per Novartis Liver Toxicity guidelines will be summarized by treatment:

The following summaries will be produced:

- ALT > 3xULN
- ALT > 5xULN
- ALT > 10xULN
- ALT > 20xULN
- AST > 3xULN
- AST > 5xULN
- AST > 10xULN
- AST > 20xULN
- ALT or AST > 3xULN
- ALT or AST > 5xULN
- ALT or AST > 8xULN
- ALT or AST > 10xULN
- ALT or AST > 20xULN
- TBL > 2xULN
- TBL > 3xULN

Combined elevations post-baseline:

For AST and ALT \leq ULN at baseline

- ALT or AST > 3xULN & TBL > 2xULN
- ALT or AST > 3xULN & TBL > 2xULN & ALP < 2xULN
- ALT or AST > 3xULN & TBL > 2xULN & ALP \geq 2xULN

For ALT or AST > ULN at baseline (Bsl)

- Elevated ALT or AST (*) & TBL (> 2x Bsl and 2xULN)
- Elevated ALT or AST (*) & TBL (> 2x Bsl and 2xULN) & ALP < 2xULN
- Elevated ALT or AST (*) & TBL (> 2x Bsl and 2xULN) & ALP \geq 2xULN

* Elevated AST or ALT defined as: >3x ULN if \leq ULN at baseline, or (>3x Bsl or 8x ULN) if > ULN at baseline

In addition, a listing of all TBILI, ALT, AST, and ALP values for subjects with a post-baseline TBILI > 2xULN, ALT > 3xULN or AST > 3xULN will be provided.

Time to onset of grade 2 or worse and time to onset of grade 3 or worse liver function test abnormalities will be summarized for the following liver function test parameters:

- AST or ALT (whichever occurs first)
- Total bilirubin

Time to onset will be summarized using Kaplan-Meier method. Median and its 95% CI will be summarized.

Time to onset of LFT abnormalities is defined as the time from the start of treatment to the start date of the first incidence of grade 2 or worse LFTs post-baseline (or grade 3 or worse), i.e., time in days is calculated as (start date of first occurrence of LFT abnormalities) – (date of first dose of study treatment) +1. A subject will be censored for time to onset if:

- the subject dies without experiencing the LFT abnormality
- the subject receives a new anticancer therapy without experiencing the LFT abnormality or before LFT abnormality has occurred
- the subject discontinues from the study treatment without experiencing the LFT abnormality (up to 130 days after study treatment discontinuation)
- the subject is still ongoing at the analysis cut-off without experiencing the LFT abnormality

The censoring date will be the earliest date from the following dates: last date of study treatment in the treatment phase + 130 days, analysis cut-off, the day before new anticancer therapy start date, death date, and last on-treatment laboratory sampling date (for the particular parameter) during on-treatment period. For the time to onset of grade 2 or worse LFTs, subjects with grade 2 or worse at baseline will be excluded from the analysis and the same for the time to onset of grade 3 or worse LFTs.

Time to onset of neutropenia and thrombocytopenia:

Time to onset of grade 2 or worse and time to onset of grade 3 or worse neutropenia and thrombocytopenia will be summarized respectively. The censoring rule will be the same as those used at time to onset of LFT abnormalities analysis.

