7.1 Study flow and visit schedule

Table 7-1 lists all of the assessments and indicates with an "X", the visits when they are performed. Each treatment cycle is 21 days (the 21 day cycle length is fixed regardless of whether the dose of canakinumab is withheld). All visits are to be scheduled according to the appropriate number of calendar days from study drug administration on Cycle 1 Day 1. A visit window of +/- 1 day in Cycle 1 and +/- 3 days in Cycle 2 onwards through EOT and Safety follow up is allowed. For Post treatment surveillance and Survival follow up, visit windows of \pm 7 days will apply in years 2 and 3, and visit windows of \pm 21 days for years 4 and 5. Imaging evaluations may be performed \pm 14 days of the due date of the assessment during years 1-3 and \pm 21 days in years 4 and 5. Note: If treatment with canakinumab/placebo is withheld or discontinued at any time during the study, all study visits, safety and efficacy assessments should continue according to the appropriate number of calendar days from Cycle 1 Day 1 as per the schedule of assessments.

Imaging assessments are to continue regardless of starting a new antineoplastic therapy after discontinuation of study treatment, if the patient has not progressed from their NSCLC or been diagnosed with new lung primary. All data obtained from these assessments must be supported in the subject's source documentation.

Subjects who discontinue from study treatment are to return for the end of treatment visit as soon as possible, and attend the follow-up visits as indicated in the Assessment Schedule

Subjects who discontinue study treatment before completing the study, and those who withdraw from the study for any reason, should be scheduled for a visit as soon as possible, at which time all of the assessments listed for the final visit will be performed.

As per Section 2.7, during a public health emergency as declared by local or regional authorities i.e. pandemic, epidemic or natural disaster that limits or prevents on-site study visits, alternative

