7.1.6 Follow up evaluations

7.1.6.1 Safety follow up

All subjects will be followed for AEs and SAEs for at least 130 days following the EOT visit. Subjects will present to the clinical site every 28 days, for a total of five follow-up visits (see Table 7-1). At the end of this period, the investigator should assess and discuss with the subject any AEs observed and concomitant medications taken since discontinuation of study treatment. Subjects whose treatment is permanently discontinued due to an AE (clinical or based on abnormal laboratory value) must be followed until resolution or stabilization of the event, whichever comes first. In case of an abnormal laboratory value, blood tests should be repeated until resolution or stabilization.

If a new antineoplastic therapy is initiated after discontinuation of study treatment, only SAEs suspected to be related to study treatment will be collected in the Adverse Events eCRF.

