-	2	116	210	307	safety follow-up 1	NA	Anytime	-
-	-	117	-	-	safety follow-up 2	NA	Anytime	-
-	3	118	211	308	safety follow-up 3	NA	Anytime	-
-	2	119	-	i.	safety follow-up 4	NA	Anytime	-
-	-	120	212	309	safety follow-up 5	NA	Anytime	-
NA	NA	1001+ ^c	2001+ ^d	3001+ ^e	NA	NA	Unscheduled and at the time of progression or AE	-

	eference ation (ID)	РК	IG Total IL-	×к IG		Scheo	luled time poin	ts (hours)
Dose ID following sampling	Dose ID prior to sampling*	sample number	sample number ^t	1β (PD) sample number ^b	Cycle	Day	Scheduled time (hours)	Description
* These dose reference IDs refer to the dose administered and dosing time of the last dose prior to collection of								

the corresponding PK, IG and PD sample. ** This collection is mandatory for all subjects that end or complete study treatment. If the subject completes

treatment, this sample will be collected pre dose for cycle 18. If the subject presents for EOT visit as a result of discontinuation, then this will be a post-dose collection relative to the last dose administered.

^a Sample should be taken immediately prior to the next administration of canakinumab.

^b IG and PD samples are to be collected together with PK samples at the same time.

° PK sample numbers for any unscheduled PK collection will start with 1001.

^d IG sample numbers for any unscheduled IG collection will start with 2001.

^e PD sample numbers for any unscheduled PD collection will start with 3001.

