7.2.6.2 PRO assessments

PRO questionnaires (EORTC QLQ-C30/LC13 and EQ-5D-5L) will be provided at the visits indicated in Table 7-1, i.e. at screening, after randomization every 3 weeks for 18 cycles, at EOT, every 4 weeks during the 130-day safety follow up, every visit before any radiological assessment is done for recurrence, before any unscheduled imaging assessments and two follow up visits after documented disease recurrence (one within 7 days and one within 28 days after discussing disease recurrence with the subject).

All questionnaires should be provided in the subject's local language at the beginning of the study visit prior to any interaction with the study investigator including any tests, treatments or receipt of results from any tests to avoid biasing the subject's perspective. This is to avoid potentially biasing subjects or their responses to study questionnaires.

PRO data will be recorded by subjects onto an electronic tablet device maintained at the study site. Investigators or study personnel should provide technical assistance but should not encourage the subjects to change responses reported in questionnaires.

Subjects should be given sufficient space and time to complete all study questionnaires. Subjects should be encouraged to complete any missing responses. Attempts should be made to collect responses to all questionnaires for all subjects, including from those who discontinue prior to the study evaluation completion visit, however, if subjects refuse to complete questionnaires, this should be documented in study source records. Subjects' refusal to complete study questionnaires are not protocol deviations.

Questionnaires should be completed before any other clinical assessments planned for the study visit.

8 Safety monitoring and reporting

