If subjects have no value as defined above, the baseline result will be missing.

On-treatment assessment/event and observation periods

For adverse event reporting the overall observation period will be divided into three mutually exclusive segments:

- **pre-treatment period:** from day of subject’s informed consent to the day before first administration of study treatment
- **on-treatment period:** from date of first administration of study treatment to 130 days (approximately five terminal half-lives of canakinumab) after date of last actual administration of any study treatment (including start and stop date)
- **post-treatment period:** starting at day 131 after last administration of study treatment.

Safety summaries (tables, figures) include only data from the on-treatment period with the exception of baseline data which will also be summarized where appropriate (e.g. change from baseline summaries). In addition, a separate summary for death including on treatment and post treatment deaths will be provided. In particular, summary tables for adverse events (AEs) will summarize only on-treatment events, with a start date during the on-treatment period (**treatment-emergent** AEs).

However, all safety data (including those from the post-treatment period) will be listed and those collected during the pre-treatment and post-treatment period will be flagged.

Windows for multiple assessments

Time windows will be defined for descriptive summary of PRO and ECOG performance status data by visit and longitudinal data analysis (Table 2-1). If more than one assessment is available in the same time window, the assessment closest to the planned date will be considered. If two assessments are obtained with the same time difference compared to the scheduled visit day, the assessment obtained prior to visit will be considered. Data obtained at the end of treatment will be classified as other assessment in the corresponding time window.

Table 2-1 Time windows for PRO and ECOG PS assessments

Time Window	Planned Visit Timing	Time Window Definition
Treatment phase		
Baseline	On or before Study Day 1[a]	≤ Study Day 1
Week 3	Study Day 22	Study Days 2 to 32
Week 6	Study Day 43	Study Days 33 to 53
.....
Week k (with k = 9, 12...)	Study Day 21*(k/3)+1	Study Day 21*(k/3)-9 to 21*(k/3)+11 If last dose date is in the window, upper bound of this time window will be EOT visit date +7

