“Note: EOT will be included if EOT is performed within 7 days of permanent discontinuation of study treatment”

Safety follow-up phase

Safety follow-up 1	26 days after treatment discontinuation	[EOT visit date+8; EOT date +39]
Safety follow-up 2	52 days after treatment discontinuation	[EOT visit date+40; EOT date +65]
Safety follow-up 3	78 days after treatment discontinuation	[EOT visit date+66; EOT date +91]
Safety follow-up 4	104 days after treatment discontinuation	[EOT visit date+92; EOT date +117]
Safety follow-up 5	130 days after treatment discontinuation	[EOT visit date+118; EOT date +143]

Post treatment efficacy follow-up phase

Post treatment follow-up (Efficacy follow up)	Every 26 weeks in Year 2 and 3; Every 52 weeks in Year 4 and 5	First time window: [upper bound of the last previous time windows with assessment + 1; TA date + TA interval at next visit/2] Otherwise : [TA date - TA interval at this visit/2; TA date+TA interval at next visit/2]
7 days post disease progression (PRO only)	Within 7 days post disease progression	[disease progression date+1; disease progression date +21]
28 days post disease progression (PRO only)	28 days post disease progression	[disease progression date+22; disease progression date +42]

[a] Study Day 1 = randomization date and PRO assessment on Cycle 1 Day1 will be baseline for PRO if randomization date is not Cycle 1 Day1.

Last contact date

The last contact date will be derived for subjects not known to have died at the analysis cut-off using the last complete date among the following (Table 2-2):

Table 2-1 Last contact date data sources

Source data	Conditions
Date of Randomization	No condition

Source data	Conditions
Last contact date/last date subject was known to be alive from Survival Follow-up page	Subject status is reported to be alive, lost to follow-up or unknown.
Start/End dates from further antineoplastic therapy	Non-missing medication/procedure term.
Start/End dates from drug administration record	Non-missing dose. Doses of 0 are allowed.
Date of disease recurrence	No condition
Laboratory/PK collection dates	Sample collection marked as 'done'.
Vital signs date	At least one non-missing parameter value
Performance Status date	Non-missing performance status
Start/End dates of AE	Non-missing verbatim term

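### The SAP's 130-day limit keeps an on-schedule fifth safety visit (days 137 to 143) out of the laboratory summaries, although the SAP's own visit window admits it

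*SAP*

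**What the plan says.** **Visit schedule.** Protocol 7.1.6.1 states: "Subjects will present to the clinical site every 28 days, for a total of five follow-up visits". Protocol 7.1.3 repeats this. Protocol 7.1 allows plus or minus "3 days in Cycle 2 onwards through EOT and Safety follow up is allowed". Table 7-1 schedules hematology and biochemistry at all five safety visits.

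**Length of follow-up.** Protocol 7.1.6.1 also says: "All subjects will be followed for AEs and SAEs for at least 130 days following the EOT visit". That is a minimum. Elsewhere 130 days is treated as the length of the period: the Table 7-1 column heading gives 28-day visits for 130 days, and Protocol 7.2.6.2 has questionnaires "every 4 weeks during the 130-day safety follow up".

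**EOT for completers.** Table 7-1 treats Cycle 18 and EOT as one visit. The footnote to Table 7-6 confirms it for subjects who complete treatment: "this sample will be collected pre dose for cycle 18". The last dose is therefore given at the EOT visit.

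**SAP timings and windows.** Table 2-1 (questionnaires and performance status) and Table 2-7 (laboratory) plan the five visits at days 26, 52, 78, 104 and 130. The last row reads "130 days after treatment discontinuation". Its analysis window runs from EOT+118 to EOT+143, and in Table 2-7 it sits under an on-treatment heading.

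**SAP cut-off.** Directly above Table 2-7, SAP 2.8.3 says: "The summaries will include all assessments available for the lab parameter collected no later than 130 days after the last study treatment administration date". SAP 2.1.1 sets the general rule: "Safety summaries (tables, figures) include only data from the on-treatment period". That period ends 130 days after the last dose.

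**What the protocol asks of the laboratory tables.** Protocol 10.5.3.3 asks for the worst post-baseline CTCAE grade with no 130-day limit, and for shift tables to the worst on-treatment value. SAP section 4 declares no change from the protocol-specified analyses.

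**The concern.** The SAP defines a place in the laboratory tables for the fifth safety visit and, in the sentence above it, excludes the values that would fill it. A programmer cannot satisfy both. Depending on which rule is coded, the Safety follow-up 5 row is either filled or nearly empty.

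The blood tests at stake are the last ones scheduled in the wash-out. They bear on late onset or persistence of neutropenia, thrombocytopenia and liver abnormalities, which are adverse events of special interest under Protocol 8.1.3. The tables affected are laboratory results by time point and the worst post-baseline grade and liver tables.

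**Working it through.** **Inputs.** Five visits, 28 days apart, counted from EOT (Protocol 7.1.6.1); window of 3 days either way (Protocol 7.1); EOT is the last-dose day for completers (Tables 7-1 and 7-6); cut-off at last dose + 130 days (SAP 2.8.3); mean terminal half-life 26 days (Protocol 1.3.1.2.3).

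**The SAP's own figure.** 5 × 26 = 130 days. This reproduces the planned day of Safety follow-up 5. It also equals five half-lives, which is the SAP's stated basis for the on-treatment period.

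**The protocol's schedule for a completer.** Visit k is due on day 28 × k.

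| Visit | SAP planned day | Protocol day | Permitted days | Table 2-7 window (days after EOT) | Permitted days on or before day 130 |
|---|---|---|---|---|---|
| 1 | 26 | 28 | 25–31 | 8–39 | 7 of 7 |
| 2 | 52 | 56 | 53–59 | 40–65 | 7 of 7 |
| 3 | 78 | 84 | 81–87 | 66–91 | 7 of 7 |
| 4 | 104 | 112 | 109–115 | 92–117 | 7 of 7 |
| 5 | 130 | 140 | 137–143 | 118–143 | 0 of 7 |

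The Table 2-7 windows capture all five visits of the 28-day schedule. Only the cut-off sentence removes visit 5. The earliest permitted day is 137 − 130 = 7 days past it, and the due date is 140 − 130 = 10 days past it.

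**How much of the visit 5 window survives.** Days 118 to 143 are 26 days. Days 118 to 130 are 13, so 13 of 26 can enter a summary, and the on-schedule days 137 to 143 all lie in the excluded half.

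**Can five visits fit in 130 days?** 130 / 28 = 4.6, so only four fit. Five would need a spacing of at most 130 / 5 = 26 days.

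**Would the SAP's own plan be safe?** The cut-off coincides with the target day. A visit planned for day 130 with 3 days either way spans 127 to 133, of which 127 to 130 are kept: 4 of 7.

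**EOT after the last dose.** Protocol 7.1.4 asks for EOT within 7 days of the last dose, or as soon as possible, after early discontinuation. At a 7-day lag, visit 5 falls on days 144 to 150 from the last dose (0 of 7 kept) and visit 4 on days 116 to 122 (7 of 7 kept).

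**The case against.** The strongest case is that the limit is deliberate. Protocol 10.5.3.1 defines the on-treatment period as ending 130 days after the last dose, and the SAP applies the same period to adverse events, laboratory data and time-to-onset censoring, with five half-lives as the reason. Extending some laboratory tables creates a second safety period: a low neutrophil count on day 140 could appear in a worst-grade table without being a treatment-emergent adverse event. This stands as a reason to keep the extension narrow. It does not explain why Table 2-7 defines an on-treatment window to EOT+143, nor does it cover the worst post-baseline tables, which the protocol does not limit to 130 days.

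A second objection is that day 140 is inferred. The protocol never prints it, and its references to a 130-day period could mean that the last visit is brought forward. A visit held by day 130 would be kept. That is fair: the protocol conflicts with itself, and the documents do not show when sites held visit 5. But moving it to day 130 breaks the 28-day interval by 10 days, against a window of 3.

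Three stronger readings are tempting and are not supported:

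- **The data are lost.** They are not. SAP 2.1.1 and 2.8.3 list all laboratory data with post-treatment values flagged, and separately list grade 3 or 4 values and the liver values of subjects with elevations.
- **Early discontinuers lose visit 4 as well.** This needs a long gap between last dose and EOT. Visit 4 is fully kept at lags of 0 to 14 days, and the protocol's target is 7.
- **The final anti-drug antibody sample is lost.** SAP 2.10.1.6 defines treatment-induced and treatment-boosted antibodies by post-baseline samples, with no 130-day limit, and plans a by-visit shift table and a listing. Only the on-treatment incidence row could be affected, and the documents do not say that it is.

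**Conclusion.** The point holds as a minor safety-reporting inconsistency. For a completer seen on the 28-day schedule, all visit 5 laboratory values, one of five follow-up visits, fall outside the summaries that Table 2-7 was built to feed. This rests on EOT being the last-dose day, on reading the schedule as 28-day intervals from EOT, and on visits being held within the stated window. At a 7-day EOT lag the result for visit 5 is the same.

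The loss is from summary tables only, by the same rule in both arms. Adverse event tables go by onset date, so an event with onset by day 130 that is reported at visit 5 still counts. Efficacy, alpha and power are unaffected.

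**What to change.** 1. In SAP 2.8.3, with a matching exception in SAP 2.1.1, let the by-time-point and worst post-baseline laboratory summaries include assessments through the Safety follow-up 5 window already defined (EOT+143).
2. Keep the 130-day limit for treatment-emergent adverse events, the shift tables to worst on-treatment value, and time-to-onset censoring, and say so explicitly.
3. Set the planned timings in SAP Tables 2-1 and 2-7 to the protocol's 28-day spacing. The windows already contain all five visits and need no change.
4. In the protocol, reconcile five visits every 28 days with the references to a 130-day follow-up, and carry the result into the SAP.

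The cost is SAP wording and one programming cut-off. No new data are needed. The small downside is that these tables reach beyond the adverse event period: 140 / 26 = 5.4 and 143 / 26 = 5.5 half-lives for a completer, and 150 / 26 = 5.8 where EOT is 7 days after the last dose. A table footnote stating the two periods would cover this.

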Viral upper respiratory tract infection	282 (12.5)	318 (13.9)	278 (12.8)	411 (12.3)
Hypertension	229 (10.1)	235 (10.3)	222 (10.2)	339 (10.1)
Angina pectoris	191 (8.4)	207 (9.1)	169 (7.8)	306 (9.1)
Back pain	189 (8.4)	202 (8.8)	171 (7.9)	301 (9.0)
Non-cardiac chest pain	190 (8.4)	196 (8.6)	157 (7.2)	304 (9.1)
Arthralgia	183 (8.1)	201 (8.8)	155 (7.1)	273 (8.2)
Upper respiratory tract infection	166 (7.3)	168 (7.4)	148 (6.8)	273 (8.2)
Bronchitis	153 (6.8)	183 (8.0)	135 (6.2)	269 (8.0)
Cough	169 (7.5)	169 (7.4)	129 (5.9)	252 (7.5)
Diarrhea	148 (6.5)	168 (7.4)	160 (7.4)	233 (7.0)
Dyspnea	157 (6.9)	147 (6.4)	137 (6.3)	236 (7.0)
Urinary tract infection	159 (7.0)	164 (7.2)	121 (5.6)	224 (6.7)
Influenza	162 (7.2)	162 (7.1)	126 (5.8)	205 (6.1)
Pain in extremity	160 (7.1)	155 (6.8)	110 (5.1)	227 (6.8)
Edema peripheral	146 (6.5)	153 (6.7)	142 (6.5)	197 (5.9)
Dizziness	128 (5.7)	138 (6.0)	145 (6.7)	212 (6.3)
Pneumonia	132 (5.8)	153 (6.7)	128 (5.9)	208 (6.2)
Headache	145 (6.4)	120 (5.3)	126 (5.8)	196 (5.9)
Fatigue	125 (5.5)	108 (4.7)	93 (4.3)	183 (5.5)
Osteoarthritis	109 (4.8)	95 (4.2)	94 (4.3)	202 (6.0)

The most common AE in CANTOS was upper respiratory infection and the most common SAE was pneumonia.

The occurrence of sepsis was reported in a slightly higher percentage of subjects 1.0-1.4 % in the canakinumab-treated groups versus 0.8% in the placebo group.

Due to the mode of action of all inhibitors of the IL-1 pathway, infection is an important concern. Subjects should be closely monitored for signs or symptoms of infection and appropriate treatment instituted in a timely manner (see Section 6.3.3). Reported infections are usually mild to moderate in severity. Although the majority of reported infections resolved spontaneously or with standard therapy, severe, serious and fatal infections have been reported. Relevant to increased infections, mild to moderate neutropenia has been reported. No CTC grade 3 or 4 episodes of neutropenia or thrombocytopenia have been reported in clinical trials with canakinumab. Inclusion/exclusion criteria (Section 5), on treatment visits and monitoring (Section 7) as well as dose adjustments (Section 6) have been included in the study protocol to mitigate these risks.

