2.5.2 Statistical hypothesis, model, and method of analysis

Assumed proportional hazards model for DFS, the following statistical hypotheses will be tested to address the primary efficacy objective:

H_{01} (null hypotheses): $\Theta_1 \geq 0$ vs. H_{a1} (alternative hypotheses): $\Theta_1 < 0$

Where Θ_1 is the log hazard ratio of DFS in the canakinumab (investigational) vs. placebo (control).

The primary efficacy analysis to test this hypothesis and compare the two arms will involve a stratified log-rank test at an overall one-sided 2.5% level of significance. The stratification will be based on the following randomization stratification factors: AJCC/UICC v8 stage IIA versus IIB versus IIIA versus IIIB with T>5cm N2 disease; Histology: squamous versus non-squamous; and Region: Western Europe and North America vs. eastern Asia vs. Rest of the world (RoW). A group sequential design is employed for the primary efficacy variable DFS. One interim analysis, along with a final analysis, is planned, using a Lan-DeMets (O'Brien-Fleming) α -spending function for efficacy and a non-binding user-defined β -spending function (gamma function with $\gamma=-3$) for futility. There is only futility assessed at the IA.

The DFS distribution will be estimated using the Kaplan-Meier method, and Kaplan-Meier curves will be plotted for each arm. The DFS Kaplan-Meier estimate along with 95% confidence intervals will be presented by year for each arm. The hazard ratio for DFS will be calculated, along with its 95% confidence interval, from a stratified Cox model using the same stratification factors as those for the log-rank test.

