2.6.4.3 Subgroup analyses for key secondary estimand

If the key secondary efficacy analysis is *statistically significant*, OS will be summarized for the subgroups specified in [Section 2.2.1](#):

- Median OS with its 95% CI from Kaplan-Meier estimation of the OS distribution
- Hazard ratio with its 95% CI using Cox proportional hazards model stratified by randomization stratification factors

A forest plot, including sample size, number of events, and HR with its 95% CI, will be produced for subgroups. *p*-values will not be generated.

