- Start date of new antineoplastic therapy before experiencing any CTC grade ≥ 2 AESI.
- Data cut-off date.
- withdrawal of informed consent date

Time to onset of CTC grade ≥ 2 AESI will be summarized using the Kaplan-Meier method by AESI grouping and treatment. Median time to onset and its 95% CI will be provided and ascending Kaplan-Meier plots will be generated by treatment. The analysis of time to onset of AESI will be performed *only* for AESI groupings of infections, opportunistic infections, neutropenia, DILI (Hepatic transaminase and bilirubin elevations) and thrombocytopenia (if there are sufficient number of events).

The same analysis will be repeated for time to onset of CTC grade ≥ 3 AESI with similar censoring rules applied.

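### SAP 2.8.3 gives a Kaplan-Meier median as the only number for time to onset of liver abnormalities, and 2.8.1.1 adds only plots for AESIs; for uncommon events that median is unlikely to be estimable, and cumulative probabilities at fixed times would serve better

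*SAP*

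**What the plan says.** SAP 2.8.3 plans time-to-onset analyses, at grade 2 or worse and at grade 3 or worse, for AST or ALT (whichever comes first) and for total bilirubin. The output is defined in two sentences: "Time to onset will be summarized using Kaplan-Meier method. Median and its 95% CI will be summarized". That passage names no plot and no estimate at a fixed time.

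The next paragraph of 2.8.3 covers the haematology parameters: "Time to onset of grade 2 or worse and time to onset of grade 3 or worse neutropenia and thrombocytopenia will be summarized respectively". It carries over the liver censoring rule and names no statistic.

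SAP 2.8.1.1 plans a parallel analysis for some AESI groupings: "Median time to onset and its 95% CI will be provided and ascending Kaplan-Meier plots will be generated by treatment". The groupings are infections, opportunistic infections, "neutropenia, DILI (Hepatic transaminase and bilirubin elevations) and thrombocytopenia (if there are sufficient number of events").

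On expected frequency, Protocol 2.6 says: "No CTC grade 3 or 4 episodes of neutropenia or thrombocytopenia have been reported in clinical trials with canakinumab". It also mentions mild to moderate neutropenia. Neither document gives an expected rate in this trial for grade 2 or worse events, or for liver abnormalities of any grade.

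**The concern.** A Kaplan-Meier median can be read off only if the estimated event-free curve falls to 0.5. For an uncommon laboratory toxicity the curve stays well above that, so the table entry would read 'not estimable' in both arms. The analysis would then say nothing about when onset occurs, or about the probability of onset after allowing for unequal time at risk. Those are the two things a censored time-to-onset analysis adds to a table of worst grades.

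At stake is the usefulness of one set of descriptive safety outputs. No hypothesis test depends on them.

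**Working it through.** The plan states no event rate, power or precision for these analyses, so there is no figure of its own to reproduce. The check asks how often a median would exist across a range of true risks.

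**Inputs**
- Subjects per arm: 1382 randomized 1:1 (Protocol, Amendment 03 rationale), so 1382 / 2 = 691.
- Observation window: 18 cycles of 21 days (Protocol 6.1.1), so the last dose falls (18 − 1) × 21 = 357 days after the first. Observation runs to 130 days after last dose (SAP 2.8.3), giving at most 357 + 130 = 487 days.
- Cumulative risk over 487 days: not in the documents; assumed 1% to 60%.
- Early treatment stopping: not in the documents; assumed 0%, 20% and 40% per year.
- Onset times exponential; log-log confidence limits, as in SAP 5.4.1; 400 simulated arms per setting.

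**How often the median exists**

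| True 487-day risk | Median estimable (range over the three stopping rates) |
|---|---|
| 1% to 40% | 0% |
| 45% | 0.3% to 1.3% |
| 50% | 47% to 54% |
| 55% | 99% or more |

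Up to a true risk of 30%, the lower confidence limit of the median was never estimable either.

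**Hand check without early stopping.** The estimate at day 487 is then a simple proportion with standard error √(p(1 − p)/n).
- p = 0.45: √(0.45 × 0.55 / 691) = 0.0189. Reaching 0.50 needs a deviation of 0.05 / 0.0189 = 2.6 standard errors, a chance of about 0.4%.
- p = 0.40: √(0.40 × 0.60 / 691) = 0.0186. The deviation needed is 0.10 / 0.0186 = 5.4 standard errors, which is effectively never.

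**The 50% rule applies to the Kaplan-Meier estimate, not to the crude share of subjects.** With 40% yearly stopping and a true risk of 55%, the crude share with an event was 47.9%, yet the median was estimable in 99% of runs.

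**What a fixed-time estimate gives instead.** Under the exponential model, risk by day 357 is 1 − (1 − F)^(357/487), where F is the 487-day risk. For F = 5% this is 1 − 0.95^0.733 = 3.7%. Simulated averages without early stopping:

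| True 487-day risk | Estimate at day 357 | Average 95% CI |
|---|---|---|
| 3% | 2.2% | 1.4% to 3.6% |
| 5% | 3.7% | 2.5% to 5.3% |
| 10% | 7.5% | 5.7% to 9.7% |
| 20% | 15.1% | 12.7% to 18.0% |

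These intervals barely change at the higher stopping rates.

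**The case against.** The other side has good points, and several stronger readings fall to them.

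- *No result for either arm.* A reader might infer this, but 2.8.3 also plans, by treatment, worst post-baseline grade, shift tables, counts above 15 liver thresholds and combined elevations. Frequency is therefore covered. Naming the Kaplan-Meier method also implies a curve could be drawn, although 2.8.3 does not ask for one. These tables give neither timing nor adjustment for censoring.
- *The median is prescribed for neutropenia and thrombocytopenia in 2.8.3.* It is not. The median sentence belongs to the liver paragraph; the haematology paragraph leaves the statistic open.
- *The AESI analysis already covers timing.* In part. It has plots by arm, but it rests on reported adverse event terms rather than laboratory grades, and the sufficient-events condition applies at least to thrombocytopenia.
- *Non-estimability is certain.* The documents do not support this. The Protocol 2.6 statement concerns only grade 3 and 4 neutropenia and thrombocytopenia. Entry limits on laboratory values do not bound later incidence. Protocol 6.3.1 calls infections the most common adverse event, so a median for grade 2 or worse infections could be reached.
- *The same defect affects the survival subgroups.* SAP 2.6.4.3 does list "Median OS with its 95% CI from Kaplan-Meier estimation of the OS distribution", while 2.5.2 says of the overall analysis: "The DFS Kaplan-Meier estimate along with 95% confidence intervals will be presented by year for each arm". But 2.6.4.3 also requires the hazard ratio with its CI and a forest plot with sample sizes and events, and runs only if OS is significant. Nor is the median out of reach in every subgroup. Protocol 1.2 puts 5-year survival in stage IIIA at about 40%. Under an exponential model the control median is 60 × ln 2 / −ln 0.40 = 45 months, or 45.4 / 0.776 = 58 months with the planned OS hazard ratio. Both precede the projected 63-month final OS analysis.

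It is also fair to say that a Kaplan-Meier median with its CI is a routine summary and that an unreached median tells the reader estimated risk stayed below 50%. For events of a few percent, the incidence tables already show that.

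**Conclusion.** The point holds for the numeric output of the liver time-to-onset analysis in 2.8.3 and of the AESI analysis in 2.8.1.1. If cumulative risk over the roughly 487-day window stays below about 45%, the median will almost always be missing in both arms. This is to be expected for uncommon liver and haematological events. It remains an expectation because the documents give no rates for this trial, and it rests on the assumed exponential onset and range of stopping rates; the result hardly varied across those rates.

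The loss is limited to the timing and the censoring-adjusted probability of onset. In the 2.8.3 haematology paragraph the gap is an unnamed statistic. The impact is low, since the output is descriptive, but the better statistic costs almost nothing. The point does not extend to the DFS or OS subgroup summaries.

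**What to change.** In SAP 2.8.3, for AST/ALT and bilirubin, replace the median as the sole number with the Kaplan-Meier cumulative probability of onset and its 95% CI by arm at fixed times from first dose, for example Weeks 12, 24 and 54. Give the number with the event and the number at risk at each time. Report the median only if it is reached. Make the same change to the numeric summary in 2.8.1.1 and keep the plots already planned there. Name the same statistic in the neutropenia and thrombocytopenia paragraph of 2.8.3.

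The listed times should all be measured from first dose. The end of the on-treatment period (last dose plus 130 days) falls at a different time for each subject, so it should not be one of them.

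The censoring rules can stay as written. The cost is a few lines of SAP wording, a list of time points in a procedure already planned, and slightly longer safety tables. No new data are needed, and nothing changes in the DFS or OS tests.
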